6.6.2. Immunogenicity Assessment

The immunogenicity assessment will be conducted to detect and measure anti-drug antibody against GS-1423 (ADA). Subjects will have ADA assessed at the designated time points as described below.

6.6.2.1. Immunogenicity Assessment in Phase 1a Cohorts

Table 6-8. Schedule of ADA Assessments for QW

| | |
|--|----------------|
| Cycle 1 Day 1 | Predose |
| Cycle 3 Day 1 | Predose |
| Cycle 4 Day 1 | Predose |
| Cycle 6 Day 1 | Predose |
| Cycle 6 Day 8 | 168 h postdose |
| At Cycle 8 Day 1 and subsequent every 12 cycles | Predose |
| 30-Day Follow-up Visit (30 days after last dose) | X |
| Posttreatment Follow-up Visit (3 months after last dose) | X |

ADA anti drug antibody against GS 1423; h hour(s); QW every week

Note: Blood will be drawn at Cycle 6, Day 8 (\pm 4 hours) even if the subject discontinues treatment at Cycle 7.

Table 6-9. Schedule of ADA Assessments for Q2W

| | |
|--|----------------|
| Cycle 1 Day 1 | Predose |
| Cycle 2 Day 1 | Predose |
| Cycle 3 Day 1 | Predose |
| Cycle 4 Day 1 | Predose |
| Cycle 4 Day 15 | 336 h postdose |
| At Cycle 6 Day 1 and subsequent every 6 cycles | Predose |
| 30-Day Follow-up Visit (30 days after last dose) | X |
| Posttreatment Follow-up Visit (3 months after last dose) | X |

ADA anti drug antibody against GS 1423; Q2W every 2 weeks

Note: Blood will be drawn at Cycle 4, Day 15 (\pm 1 day) even if the subject discontinues treatment at Cycle 5.

[figure not shown]
Table 6-10. Schedule of ADA Assessments for Q3W

| | |
|--|----------------|
| Cycle 1 Day 1 | Predose |
| Cycle 2 Day 1 | Predose |
| Cycle 3 Day 1 | Predose |
| Cycle 3 Day 22 | 504 h postdose |
| Cycle 6 Day 1 | Predose |
| At Cycle 8 Day 1 and subsequent every 4 cycles | Predose |
| 30-Day Follow-up Visit (30 days after last dose) | X |
| Posttreatment Follow-up Visit (3 months after last dose) | X |

ADA = anti drug antibody against GS 1423; Q3W = every 3 weeks

Note: Blood will be drawn at Cycle 3, Day 22 (\pm 1 day) even if the subject discontinues treatment at Cycle 4.

CCI

CCI

CCI

CCI

The document page is heavily redacted. A large black rectangular redaction box covers the top half of the page. Below this, there are several smaller redaction boxes: one on the left side, one spanning the middle section, and two on the right side. The redaction boxes are solid black and completely obscure the underlying text.

CCI

CCI

CCI

CCI

CCI

CCI

6.7. End of Study

End of study will be defined as when the last subject reaches the last scheduled follow-up time point (including posttreatment or survival), or lost to follow-up, withdraws from the study, dies, or the time at which Gilead closes the study.

6.8. Posttreatment Assessments

6.8.1. End-of-Treatment Phase Visits

End-of-Treatment requirements are outlined in [Appendix 2](#). There is an End-of-Treatment Visit within 7 days of last dose of study treatment and a 30-Day Follow-up Visit which occurs 30 days (± 7 days) after last dose of study treatment.

6.8.1.1. End-of-Treatment Visit

The End-of-Treatment Visit should occur at the time all study drug is permanently discontinued for any reason. If the End-of-Treatment Visit occurs 30 days from the last dose of study treatment, at the time of the mandatory 30-Day Follow-up Visit, procedures do not need to be repeated. Procedures at the time of discontinuation are detailed in 30-Day Follow-up Visit, Section [6.8.1.2](#). Subjects who discontinue from the study treatment for reasons other than PD will continue to have imaging/computed tomography (CT) scans at the predefined schedule until documented PD or initiation of a new anticancer treatment.

6.8.1.2. 30-Day Follow-up Visit

The mandatory 30-Day Follow-up Visit should be conducted for all subjects approximately 30 days after the last dose of study treatment or before the initiation of a new anticancer treatment, whichever comes first. Subjects with an AE of Grade > 1 will be further followed until the resolution of the AE to Grade 0 or 1 or until initiation of a new anticancer therapy, whichever occurs first.

6.8.2. Posttreatment Follow-up Phase Visits

All subjects who discontinue study treatment will have at least 1 posttreatment visit at 3 months (± 7 days) from last dose of study treatment. Subjects who discontinue all study treatment for any reason other than PD and/or start of new anticancer therapy will have imaging/CT scans at the predefined schedule until documented PD or initiation of a new anticancer treatment. Subjects who discontinue study drug treatment due to PD and/or start of a new anticancer therapy will not require imaging/CT scans and will move into Survival Follow-up thereafter.

Subjects who have discontinued all study drug treatment due to reasons other than PD and/or start of a new line of therapy should be followed with Posttreatment Follow-up Visits for up to 12 months from last study treatment dose or until PD and/or start of a new line of therapy. Every effort should be made to collect subject information on the start of new anticancer therapy, PD, and death.

6.8.3. Survival Follow-up

After the first Posttreatment Follow-up visit, subjects who present(ed) with PD and/or start(ed) a new anticancer therapy will move into Survival Follow-up. Subjects should be contacted by telephone to assess for survival status every 3 months for up to 12 months. No imaging assessment is required for Survival Follow-up. Information about deaths solicited during the Survival Follow-up Period should be reported, but will not be considered or reported as SAEs. Investigators should abide by the reporting obligations as stated in Section 7.

6.9. Assessments for Early Discontinuation from Study

If a subject discontinues study dosing (for example, as a result of an AE), every attempt should be made to keep the subject in the study and continue to perform the required study-related follow-up and procedures (see Section 6.10.1, Criteria for Discontinuation of Study Treatment). If this is not possible or acceptable to the subject or investigator, the subject may be withdrawn from the study.

6.10. Criteria for Discontinuation from Treatment or Study

6.10.1. Criteria for Discontinuation from Treatment

Discontinuation of treatment does not represent withdrawal from the study.

As certain data on clinical events beyond treatment discontinuation may be important to the study, they must be collected through the subject's last scheduled follow-up (including 30-Day Follow-up or Posttreatment visits), even if the subject has discontinued treatment. Subjects may discontinue treatment at any time for any reason or be dropped from treatment at the discretion of the investigator should any untoward effect occur. In addition, a subject may be discontinued from treatment by the Investigator or by Gilead if treatment is inappropriate, the trial plan is violated, or for administrative and/or other safety reasons.

Specific details regarding procedures to be performed at treatment discontinuation are provided in the Study Procedures Tables ([Appendix 2](#)). A subject must be discontinued from treatment but continue to be monitored in the trial for any of the following reasons:

- The subject or subject's legally acceptable representative requests to discontinue treatment for any reason.
- Occurrence of an event that would have been considered an exclusion criterion prior to enrollment, that is clinically relevant and affects the subject's safety, and if discontinuation is considered necessary by the investigator and/or Gilead.
- Intercurrent illness that would, in the judgment of the investigator, affect assessments of clinical status to a significant degree.
- Investigator's decision to discontinue the subject
- Initial PD, defined by RECIST 1.1 (Section [6.11.1](#)), unless the subject is considered to derive clinical benefit from the treatment by the investigator, is clinically stable, and there is agreement with Gilead (Section [5.5.7](#)).
- Therapeutic failure (i.e. clinical disease progression)
- Recurrence of previously treated malignancy or any occurrence of another malignancy that requires active treatment
- Pregnancy during the study
- Noncompliance with trial treatment or procedure requirements (Section [5.5.6.1](#))
- Use of a non-permitted concomitant drug, as defined in Section [5.6.2](#), for which the predefined consequence is withdrawal from study drug (Gilead may be contacted to discuss whether study treatment must be discontinued).
- Any requirement for > 10 mg of prednisone per day or equivalent for more than 6 weeks
- Dose delay of GS-1423 which results in no GS-1423 dosing for more than 4 weeks (QW or Q2W) or 6 weeks (Q3W)
- Discontinuation of the study at the request of Gilead, a regulatory agency, or an IRB/IEC
- Any AE and/or laboratory abnormality in the judgment of the investigator, presents a substantial clinical risk to the subject with continued treatment
- AEs specifically described in Section [5.5.6](#) must lead to study drug discontinuation.

NOTE: Tumor flare phenomenon, defined as local pain, irritation, or rash localized at sites of known or suspected tumor does not require treatment discontinuation.

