3.2.3.3. Definition of Dose Limiting Toxicity

Toxicity will be graded according to National Cancer Institute Common Terminology Criteria for Adverse Events Version 5.0 (NCI CTCAE v5.0). A DLT is a toxicity observed in the first 28 days as defined below and considered possibly related to GS-1423.

A DLT may lead to permanent withdrawal of GS-1423 for the subject after discussion between the Investigator and Gilead.

Hematologic

- Grade 3 thrombocytopenia with clinically significant bleeding (ie, requires hospitalization, transfusion of blood products, or other urgent medical intervention)
- Grade ≥ 3 febrile neutropenia (absolute neutrophil count [ANC] $< 1.0 \times 10^9/L$ and fever $> 101^{\circ}\text{F}/38.3^{\circ}\text{C}$)
- Any Grade 4 hematologic laboratory abnormalities/AEs regardless of duration will be considered DLTs with the **exception** of

Grade 4 lymphopenia

Grade 4 neutropenia lasting ≤ 7 days that is not associated with fever (the use of growth factors is permitted)

Grade 4 anemia explained by underlying disease

Non-Hematologic

- Grade 4 non-hematologic (laboratory and non-laboratory) AEs will be considered DLT regardless of the duration
- Any \geq Grade 2 uveitis, blurred vision, eye pain, and/or reduction of visual acuity that does not respond to topical therapy and does not improve to Grade 1 severity within 2 weeks of the initiation of topical therapy OR requires systemic treatment will be considered as a DLT
- The following Grade 3 non-hematologic AEs **will be considered as DLTs**:

Any Grade 3 AE of unknown etiology consistent with an immune phenomenon that does not resolve to \leq Grade 1 or to baseline with immunosuppressive therapy within 3 weeks of its onset

Any Grade 3 central nervous system (CNS)-related AE of unknown etiology consistent with an immune phenomenon regardless of duration or reversibility

Alanine aminotransferase (ALT) or aspartate aminotransferase (AST) elevation $\geq 3 \times$ upper limit of normal (ULN), also showing elevation of serum total bilirubin of $> 2 \times$ ULN, without initial findings of cholestasis (elevated serum alkaline phosphatase)

- Any other non immune-related Grade 3 AE **except:**

Any Grade 3 endocrinopathy that is adequately controlled by hormonal replacement
Grade 3 AE of tumor flare (defined as local pain, irritation, or rash localized at sites of known or suspected tumor)

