5.5.5. Criteria to Resume Treatment

Subjects may resume treatment with GS-1423 when drug-related AE(s) resolve(s) to Grade 1 or baseline value, with the following exceptions:

- Subjects may resume treatment in the presence of Grade 2 fatigue.

- Subjects with combined Grade 2 AST/ALT **and** total bilirubin values lasting > 7 days meeting discontinuation parameters (Section 5.5.6) should have treatment permanently discontinued.
- Drug-related Grade 2 pulmonary toxicity or colitis must have resolved to baseline before treatment is resumed.
- Drug-related endocrinopathies adequately controlled with only physiologic hormone replacement may resume treatment. (Exception: Study treatment does not need to be delayed/interrupted for subjects who experience immune-related hypothyroidism [Grades 1-2].)
- Subjects who received systemic corticosteroids for management of any drug-related toxicity must be off corticosteroids or have tapered down to an equivalent dose of prednisone \leq 10 mg/day.

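### The tumor flare NOTE in Protocol Section 6.10.1 has no grade limit; read as an exception, it removes the automatic Table 5-10 stop for drug-related Grade 4 flare

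*Protocol*

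**What the plan says.** Protocol Section 6.10.1 lists the reasons for which a subject has to come off treatment. Its last bullet says that the AEs described in Section 5.5.6 "must lead to study drug discontinuation". The NOTE directly beneath reads: "Tumor flare phenomenon, defined as local pain, irritation, or rash localized at sites of known or suspected tumor does not require treatment discontinuation". It sets no limit on grade, duration, recurrence or drug relatedness.

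Section 5.5.6 is also mandatory for the drug-related AEs in Table 5-10. Four entries can touch flare as the NOTE defines it:
- a Grade 4 non-hematologic AE;
- recurrence of a Grade 3 or higher AE;
- a Grade 2 or 3 AE not resolved within 12 weeks;
- a Grade 3 or higher skin AE, which matters because rash is part of the flare definition. Section 5.5.2 repeats this stop.

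The footnote to Table 5-10 limits it to drug-related events. There is no flare exception. Section 5.5.6 sends the reader to Section 6.10.1 only for reasons other than AEs, and neither section says which text prevails.

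Section 3.2.3.3 treats flare more narrowly. Its exceptions to the DLT definition include flare at Grade 3 only, while a Grade 4 non-hematologic AE is a DLT whatever its duration.

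**The concern.** A mandatory list and an unqualified exemption stand next to each other with no rule of precedence. A site working from Table 5-10 would stop a related flare that meets an entry, and is not pointed to the NOTE. A site working from Section 6.10.1 could treat the same flare as exempt.

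The Grade 4 case matters most. The protocol limited its flare exemption to Grade 3 when defining DLTs but set no such limit for stopping treatment. If the NOTE is an exception, a related Grade 4 flare in the DLT window would count as a DLT and yet not require withdrawal by rule, since Section 3.2.3.3 says only: "A DLT may lead to permanent withdrawal of GS-1423 for the subject after discussion between the Investigator and Gilead". What is at stake is an automatic safety stop, and consistency between sites in why subjects come off GS-1423.

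**Working it through.** The plan gives no figure to reproduce, so the check sets the texts side by side.

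**1. The four Table 5-10 entries under each reading, for drug-related flare**

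| Entry | Can flare meet it? | NOTE is an exception | Table 5-10 governs |
|---|---|---|---|
| Grade 4 non-hematologic AE | Depends on how the term is graded (step 2) | No automatic stop | Stop |
| Recurrent Grade 3 or higher AE | Yes; Section 3.2.3.3 itself foresees Grade 3 flare | No automatic stop | Stop |
| Grade 2 or 3 AE unresolved after 12 weeks | Yes, mainly if dosed through (step 4) | No automatic stop | Stop |
| Grade 3 or higher skin AE (also Section 5.5.2) | Yes, for flare rash, at first occurrence | No automatic stop | Stop |

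Flare judged unrelated to study drug falls outside Table 5-10 on either reading.

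**2. Can flare be Grade 4?** Section 7.2.2 grades AEs by CTCAE v5.0. Its general scale, where Grade 4 covers life-threatening or disabling events, applies only where CTCAE does not grade the term specifically. Protocol Appendix 4 is only a link to CTCAE. The documents therefore leave open whether a given flare term has a Grade 4.

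**3. Do the other rules reproduce the Grade 4 stop?** Take a related Grade 4 flare on the every-2-weeks schedule that settles to Grade 1 soon enough for dosing to restart within 4 weeks of the last dose.
- Section 5.5.5: "Subjects may resume treatment with GS-1423 when drug-related AE(s) resolve(s) to Grade 1 or baseline value". Satisfied, so resumption is allowed.
- No-dosing stop in Section 6.10.1 (more than 4 weeks): not reached.
- Steroid stop in Section 6.10.1, "Any requirement for > 10 mg of prednisone per day or equivalent for more than 6 weeks": not reached if steroids are brief.
- DLT discussion (Section 3.2.3.3): applies only to the first 28 days.
- Substantial-risk bullet in Section 6.10.1: once the investigator judges continued treatment a substantial clinical risk, stopping is mandatory.

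On the exception reading, only the last item can compel a stop after day 28, and it depends on judgment. Section 5.5.1.1 does not permit dose reduction, so any re-dosing would be at the same dose.

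**4. The 12-week entry.** If GS-1423 is held from onset and the flare does not return to Grade 1 or baseline, Section 5.5.5 bars resumption and the no-dosing stop applies after 4 weeks (weekly or every 2 weeks) or 6 weeks (every 3 weeks). Since 4 < 12 and 6 < 12, that stop comes first. The 12-week entry adds something mainly when a flare is dosed through.

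**5. Dose-finding and reporting.** Section 3.2.3.3 defines DLTs independently of the NOTE, so DLT and MTD determination is unchanged. The SAP (Section 1) covers Phase 1a Part A only, because the study ended there. Any difference would show mainly in the descriptive summaries of treatment-emergent AEs leading to premature discontinuation of GS-1423 (SAP Section 7.1.6.1).

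**The case against.** The strongest reply is that the NOTE is a specific statement placed directly under the bullet that brings in Section 5.5.6, so it is naturally read as an exception to that bullet. It is also permissive: it says stopping is not required and does not tell anyone to continue. Both points stand. A reader might infer that sites are given opposite instructions. The documents do not support that, because a site that stops under Table 5-10 breaches nothing in Section 6.10.1.

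A reader might also infer that a subject with a dangerous flare could be kept on drug with no mandatory stop. That is not supported either. The substantial-risk bullet applies on both readings, and Section 6.10.1 adds that "a subject may be discontinued from treatment by the Investigator or by Gilead if treatment is inappropriate". Nor can it be said from Section 7.2.2 that disabling local pain is Grade 4, since the general scale is only a fallback.

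One thing survives. Accepting the NOTE as an exception is exactly what takes away the automatic Grade 4 stop, and nothing in the protocol explains why flare should be limited to Grade 3 for DLTs but unlimited for discontinuation.

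**Conclusion.** The concern holds as a minor drafting defect. The NOTE has no grade limit, Table 5-10 has no flare exception, and no text ranks them. On the most natural reading, the automatic stop for a related Grade 4 flare becomes a matter of investigator judgment, out of step with the Grade 3 limit in Section 3.2.3.3. The skin, recurrence and 12-week entries are also left open, but whether flare should be exempt from those is a clinical choice the sponsor may already have meant to make.

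The practical size is small. The mandatory substantial-risk stop remains, DLT and MTD are untouched, and the reporting effect is descriptive. The documents give no flare frequency, so no number of subjects or doses is claimed. The conclusion rests on two assumptions: that the flare is judged drug-related and, for the Grade 4 case, that the reported term can be graded 4 under CTCAE v5.0 or, where CTCAE does not grade it, the general scale.

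**What to change.** 1. Reword the NOTE in Section 6.10.1, keeping the present definition of flare in parentheses after the grade limit: *Tumor flare of Grade 3 or lower does not by itself require treatment discontinuation; drug-related Grade 4 tumor flare requires discontinuation per Table 5-10.*
2. In Section 5.5.6, extend the existing pointer to Section 6.10.1 so that it also mentions the note on tumor flare.
3. Have the sponsor state whether the NOTE or Table 5-10 governs related flare of Grade 3 or lower that meets the skin, recurrence or 12-week entry. Until that is stated, Table 5-10 should be the default. Making every Table 5-10 entry override the NOTE permanently would leave the NOTE with nothing to exempt from that table, so the decision belongs to the sponsor.

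The cost is one reworded sentence, one pointer clause and one statement of precedence. There are no added procedures or subjects, Section 3.2.3.3 needs no change, and items 1 and 2 and the default loosen no safety stop.

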6.10.2. Discontinuation from Disease Response Evaluation

Tumor evaluation will be discontinued if any of the following occurs:

- In a subject who does not meet the criteria to continue study drug treatment beyond initial RECIST 1.1-defined PD (Section [5.5.7](#)).
- In a clinically stable subject (defined in Section [5.5.7](#)), at the time of PD is assessed in a second, consecutive assessment (using the same imaging modality) no less than 4 weeks from previous imaging assessment.
- Initiation of new anticancer therapy

6.10.3. Criteria for Discontinuation from Study

Subjects should be discontinued from the study for 1 or more of the following:

- Withdrawal of consent
- Lost to follow-up
- Death
- Subject noncompliance (Section [5.5.6.1](#))
- Administrative study closure

6.11. Efficacy Assessments

6.11.1. Response Assessment

Response assessment will be performed according to RECIST 1.1 {[Eisenhauer 2009](#)}.

For all subjects, tumor response assessment will be performed by CT or magnetic resonance imaging (MRI) of the chest/abdomen/pelvis (plus other regions as required for specific tumor types) and other established assessments of tumor burden if CT/MRI imaging is insufficient for the individual subject. All scans performed at baseline and other imaging performed as clinically required (other supportive imaging) will be repeated at subsequent visits. In general, lesions detected at baseline should be followed using the same imaging methodology and preferably the same imaging equipment at subsequent tumor evaluation visits.

For each subject, the investigator will designate 1 or more of the following measures of tumor status to follow for determining response: CT or MRI images of primary and/or metastatic tumor masses, physical examination findings, and results of other assessments. All available images collected during the study period will be considered. The most appropriate measures to evaluate a subject's tumor status should be used. Measure(s) chosen for sequential evaluation during the

study must correspond to measures used to document progressive tumor status that qualifies the subject for enrollment.

Subjects who experience initial radiologic PD and are doing well clinically are considered to have initial RECIST 1.1-defined PD and will be permitted, with Gilead's approval, to continue with study drug treatment (see Section 6.11.2). These subjects will be reevaluated using the same imaging modality no less than 4 weeks later to assess whether study drug treatment will be continued. If initial progression is based on occurrence of a new lesion in an area not scanned at baseline, an on-study scan no less than 4 weeks from initial observation of new lesion should be considered before performing the End-of-Treatment Visit.

Tumor responses to treatment will be assigned based on evaluation of response of target, non-target, and new lesions according to RECIST 1.1 (all measurements should be recorded in metric notation; see {Eisenhauer 2009}). To assess objective response, tumor burden at baseline will be estimated and used for comparison with subsequent measurements. At baseline, tumor lesions will be categorized in target and non-target lesions as described in {Eisenhauer 2009}.

Results for these evaluations will be recorded with as much specificity as possible so that pretreatment and posttreatment results will provide the best opportunity for evaluating tumor response.

Any complete response (CR) or partial response (PR) should be confirmed by CT or MRI scan as described in {Eisenhauer 2009} no less than 28 days after initial assessment.

The investigator may perform scans in addition to a scheduled study scan for medical reasons or if PD is suspected.

